#### **5. PROCEDURES INVOLVED**

QUARTET USA is a phase II, two-arm, randomized (1:1 allocation), double-blind clinical trial. Study participation involves the following study visits: (1) a two-day screening and baseline visit (including 24-hour ABPM and randomization if eligible), (2) six-week follow-up visit, and (3) 12-week follow-up visit. We do not plan for any long-term follow-up data at this time. After participants complete all procedures in their 12-week visit and return their ABPM, they will exit the study, and we plan to stop data collection for them at that time.

To monitor safety, we will document all adverse events in case report forms (CRFs) with expedited reporting for adverse events meeting criteria as defined by regulatory authorities (e.g., MedWatch form for SAEs that are probably or definitely related to the study drug and unexpected). We plan to perform centralized monitoring of all essential study data with targeted on-site visits as appropriate (refer to the DSMP and Adverse Event Reporting Plan for details). An external DSMB will also review all essential outcome and safety data every six months at minimum.

The following study visit matrix explains the research procedures and assessments / data collected at each visit. Full description of procedures and assessments is included within the Manual of Procedures.

REDCap Event			
Study Timeline	Screening and Randomization	6-Week Follow-up Visit	12-Week Follow-up Visit
Visit Window from Previous Visit	-12 weeks	+/- 7 days	+/- 7 days
Location	Clinic with telehealth screening and eConsent option	Clinic	Clinic
Study Activities			
Informed consent	X 		
Demographics 	X 		
Automated office (clinic) blood pressure measured in the previous 12 weeks	X 		
Blood pressure and heart rate measurements, by research team	X	X	X
ECG	X 		
Anthropometrics and Medical history	X 		
Concomitant medications	X 	X	X
Lifestyle questions	X 		
PROMIS global health	X 		X
Laboratory assessments 	X 	X	X
24-hour ABPM	X		X
Inclusion and exclusion criteria	X 		
Randomization	X		
Study Drug dispense	X	X	
Study Drug return		X	X
Medication adherence		X	X
Participant status		X	X
Health service utilization		X	X
AEs and SAEs	X	X	X

This form may be completed electronically via a telehealth visit up to 90 days before the date of randomization (12 weeks in the case of previous automated office blood pressure measurement).

Such as date of birth, sex, and ethnicity.

If these tests completed within 3 months of the screening visit, and the results are available, then these tests will not be required at this visit.

Urine test and blood tests. Blood tests include sodium, potassium, chloride, bicarbonate, urea, serum creatinine, estimated glomerular filtration rate, AST, ALT, glucose, low density lipoprotein cholesterol, high density lipoprotein

cholesterol, total cholesterol, and triglycerides. Urinary analysis include hCG (for women only) and urinary albumin and creatinine for both men and women. For women, urine test is required to rule out pregnancy.

Laboratory assessments, concomitant medications, and medical history will be obtained from the electronic health record (EHR), which will be considered source for these assessments.

If a telehealth visit is conducted prior to randomization, then all information collected during these visits will be documented electronically, including the consent as outlined in the Consent Process section of the protocol. During the in-person screening and randomization visits, the electronic information will be verified and documented on paper CRFs. Any updates to previously reported information will be made at that point in time both electronically and if necessary, on paper versions of CRFs in accordance with Good Clinical Practice guidelines.

Other study-related data indicated in the visit schedule above will be collected via paper CRFs, which will serve as source documents. The data from the paper CRFs and EHR will be entered electronically into REDCap, housed at Northwestern University. See the appendix for current CRFs. We plan to use a “first / second pass” workflow, whereby one study team member will enter study data into the eCRFs and leave the data as “unverified”. Then, a second study team member will review the data entered for accuracy and consistency in comparison to the EHR and paper CRFs. If there are any queries, then he / she will use the Data Resolution Workflow module in REDCap to resolve these issues. If there are no queries or data issues noted, then the second pass study team member will mark the form(s) as “complete”. All study data must be entered into the electronic database within two business days after collection on paper CRFs. AEs may be deemed an exception to this rule as they have separate reporting requirements as outlined in the AE Reporting Plan and Data and Safety Monitoring Plan.

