### 3.3. Tolerability & Safety

- a. Percentage of participants with any SAE according to GCP definition.
- b. Percentage of participants with any potentially relevant side effect (refer to the adverse event case report form and the list of relevant side effects from the informed consent form, included as an Appendix).
- c. Rate of relevant side effects at the participant level.
- d. Mean change (from baseline) in continuous serum potassium (mEq/L).
- e. Mean change (from baseline) in continuous serum sodium (mEq/L).
- f. Mean change (from baseline) in continuous blood urea nitrogen (mg/dl).
- g. Mean change (from baseline) in continuous serum creatinine (mg/dl).

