#### **4. STUDY INTERVENTION**

Patients who are eligible to participate in the trial will be randomized (1:1 allocation) to one of two study arms, and they will take daily:

1. Low Dose Quadruple Therapy (LDQT) comprising candesartan 2 mg, amlodipine 1.25 mg, indapamide 0.625 mg, and bisoprolol 2.5 mg  
OR
2. Candesartan 8 mg

The LDQT includes quarter standard doses of four blood pressure lowering medications, which are currently approved by the US Food and Drug Administration for the treatment of hypertension. The active comparator follows current clinical practice guidelines for the majority of Americans, initiating treatment with an angiotensin II receptor blockers (ARB), which has the best side effect profile of any blood pressure lowering therapy. In both arms, if blood pressure is not controlled (SBP > 130 mmHg or DBP > 80 mmHg) at the six-week follow-up assessment, then study staff will provide participants with an open label pill of amlodipine 5 mg to supplement their study drug, which may be relevant to participants from some race/ethnic groups, including African-Americans. The combination of a calcium channel blocker with an ACE-inhibitor has been demonstrated to be more effective in reducing cardiovascular events than the combination of a thiazide-like diuretic with an ACE-inhibitor based on the ACCOMPLISH trial.

All study drugs, including LDQT, active comparator, and amlodipine add-on will be stored, controlled, and administered centrally. Control of drugs is described in full in the detailed Manual of Procedures. Drug product used in this study is subject to regulatory review and approval through an investigator-initiated investigational new drug (IND) process. Prior to use in human subjects, IND approval will be required.

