## **9.2. Exclusion criteria:**

- Known contraindication to candesartan, amlodipine, indapamide or bisoprolol.
- Previous diagnosis of coronary artery disease, stroke, or heart failure.
- Presence of significant proteinuria (based on 3+ proteinuria via spot urinalysis or >300 mg/dL of proteinuria based on random urinary albumin-to-creatinine ratio testing of 300 mg/g)
- Evidence of secondary cause of hypertension e.g., renal artery stenosis; significant renal impairment (eGFR <50 ml/min/1.73 m^2), raised serum potassium (above lab normal limit of 5.5 mEq/L).
- Women who are pregnant, breast feeding or of childbearing potential and are not using and do not plan to continue using medically acceptable form of contraception throughout the study (pharmacological or barrier methods).
- Concomitant illness, physical impairment or mental condition which in the opinion of the study team / primary care physician could interfere with the conduct of the study including outcome assessments.
- Participation in a concurrent interventional medical investigation or pharmacologic clinical trial. Patients in observational, natural history or epidemiological studies not involving an intervention are eligible.
- Participant's responsible primary care or other responsible physician believes it is not appropriate for participant to switch current monotherapy.
- Inability or unwillingness to provide written informed consent.
- Unable to complete study procedures.

This study will not include any of the following special populations: a) adults unable to consent; b) individuals who are not yet adults (minors): i.e. infants, children, or teenagers; c) pregnant women; or d) prisoners or other detained individuals.

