Irregular or slow heartbeat		Very common		Common
Loss of appetite				Common
Muscle aches and pains		Common		Common
Muscle cramps or spasms				Common
Nausea, vomiting	Uncommon	Common	Common	Uncommon
Passing less urine			Common	
Redness, blistering, peeling or loosening of the skin, including inside the mouth				Very rare
Stomach gas, pain	Common		Common	
Sweating		Uncommon		
Swelling of hands or feet			Uncommon	
Swelling of legs or ankles	Very common	Uncommon		
Tremors		Uncommon		
Trouble sleeping	Uncommon			
Unusually weak or tired	Uncommon			Common

- In addition to these risks, this research may harm participants in ways that are unknown. These may be a minor inconvenience or may be so severe as to cause death but this is not expected.
- This study involves the use of participants' identifiable, personal health information and there is a chance that a loss of confidentiality could occur. The researchers have procedures in place to lessen the possibility of this happening.
- The study drug may also hurt a pregnancy or fetus in ways that are unknown. These may be a minor inconvenience or may be so severe as to cause death. Participants currently pregnant or nursing will be excluded from this study, and eligibility is contingent on participants' willingness to use acceptable forms for birth control. If participants become pregnant during the course of the study, then they are asked to notify the study team, and the study team will halt study drug administration. The study team will

continue to follow these participants and collect any AE and study-related data through the final study time point.

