- 2) Proportion of participants with *any* potentially relevant side effect ([sae_term] refer to the adverse event case report form and the list of relevant side effects from the informed consent form).
- 3) Rate of relevant side effects at the participant level (i.e., count per participant [sae_term]).
- 4) Mean change (from baseline) in continuous serum potassium (mEq/L), controlling for baseline value [potassium].
- 5) Mean change (from baseline) in continuous serum sodium (mEq/L), controlling for baseline value [sodium].
- 6) Mean change (from baseline) in continuous blood urea nitrogen (mg/dl), controlling for baseline value [urea].
- 7) Mean change (from baseline) in continuous serum creatinine (mg/dl), controlling for baseline value [creat].

Exploratory Outcomes

The following outcomes are relevant to the overall aims; however, they carry less weight, and we consider them exploratory in nature. This SAP will not focus in detail on analyses of these outcomes, but we anticipate the general analytic approach to apply. In the event of small numbers that would make modeling infeasible, these data may be reported as descriptive statistics.

ABPM measures

24-hour ambulatory blood pressure monitor (ABPM) measures at 12 weeks adjusted for baseline values:

- 1) Mean 24-hour SBP and DBP [overall_abpsbp, overall_abpdpb].
- 2) Mean daytime (0600 to 2200) [awake_abpsbp, awake_abpdpb] SBP and DBP.
- 3) Mean nighttime (2200 to 0600) SBP and DBP [asleep_abpsbp, asleep_abpdpb].
- 4) Proportion of dippers [sys_dip, dia_dip], defined as nighttime BP falling more than 10% from the daytime values OR night / day blood pressure ratio less than 0.9 and greater than 0.8 with normal diurnal blood pressure pattern.
- 5) Mean daytime SBP and DBP load. Load is defined as the percentage of abnormally elevated readings; daytime SBP / DBP elevated readings would be 130 / 80 mmHg or above.
- 6) Mean nighttime SBP and DBP load. Abnormally elevated readings for nighttime SBP / DBP would be 120 / 70 mmHg or above.
- 7) Percentage of participants with morning surge, calculated as the difference between the mean SBP during the morning hours and nighttime trough SBP. Trough SBP is defined as the mean of three SBP measurements: the lowest nighttime SBP and the measurements immediately preceding and following this measurement.

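### Heart rate is measured at every visit but is not an outcome, although only LDQT contains bisoprolol; laboratory safety is mean change only, with no by-arm count of out-of-range values

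*Protocol*

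**What the plan says.** **Treatment.** Protocol section 4 defines the intervention as "Low Dose Quadruple Therapy (LDQT) comprising candesartan 2 mg, amlodipine 1.25 mg, indapamide 0.625 mg, and bisoprolol 2.5 mg"; the comparator is candesartan 8 mg. In either arm, if blood pressure is not controlled at week 6, "study staff will provide participants with an open label pill of amlodipine 5 mg to supplement their study drug".

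**Collection.** The visit matrix in Protocol section 5 marks "Blood pressure and heart rate measurements, by research team" at all three visits. Laboratory tests are also marked at all three. The ECG is marked at screening only.

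**Known risks.** The side-effect table in Protocol section 14 lists "Irregular or slow heartbeat" as very common for bisoprolol and common for indapamide; the candesartan cell is blank. The section states that the frequencies come from standard doses, and that a listed effect occurring during the trial will be reported as an adverse event.

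**Outcomes.** Protocol 3.3 and SAP section 2 name the same seven safety outcomes: any SAE, any relevant side effect, the rate of relevant side effects, and change in potassium, sodium, urea nitrogen and creatinine. The SAP wording for the first analyte is "Mean change (from baseline) in continuous serum potassium (mEq/L), controlling for baseline value", and the other three follow the same form. The SAP modelling table treats all four as continuous with an identity link. Heart rate is not among the safety, secondary or exploratory outcomes, nor in that table.

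**The concern.** The trial means to draw a tolerability conclusion. Protocol section 1 expects fewer side effects with LDQT, and SAP Aim 1 expects no more than with monotherapy. Bisoprolol is one of the drugs that distinguishes the arms, and its listed effect on heart rhythm has an objective measure that staff already take at every visit. As planned, that measure has no by-arm analysis. A low rate without symptoms counts only if someone records it as an adverse event, and it is then one item within a composite of side effects.

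The laboratory outcomes have a related weakness. An arm mean can stay flat while one participant's potassium or sodium moves well outside the laboratory's limits, or while high and low values cancel. The protocol's 5.5 mEq/L potassium limit appears as an entry criterion, but no safety outcome in either document uses it.

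**Working it through.** The plan gives no figure on this point to reproduce. The check is mainly a comparison of lists, followed by arithmetic to show scale.

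**1. Where heart rate could appear**
- Protocol 3.1 to 3.4: absent.
- SAP section 2 (primary, secondary, safety, exploratory): absent.
- SAP section 6 modelling table: no row.
- Central monitoring (Protocol section 16): outlying values are summarised overall and by site, and the reports are explicitly not split by arm.
- DSMB reports (SAP section 10): descriptive statistics on primary and safety outcomes. Heart rate is not a listed safety outcome, so a by-arm table is not assured.

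**2. Where slow heartbeat does appear**
- As a reported adverse event, counted in any relevant side effect and in the rate of relevant side effects. The protocol's side-effect table has 32 rows, so if the consent-form list matches it, slow heartbeat is 1 of 32 items in a pooled outcome. None of the 32 rows is a laboratory abnormality.

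**3. Very common entries in the table**
- Feeling faint, lightheaded or falling: candesartan, in both arms.
- Irregular or slow heartbeat: bisoprolol, in LDQT only.
- Swelling of legs or ankles: amlodipine, in LDQT from randomisation and in controls only as the conditional add-on from week 6.

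**4. Precision of a heart-rate comparison**
- Analysed sample: 87 × (1 − 0.12) = 76.6, matching the stated 77, or 38.5 per arm.
- Assumed, because the documents give neither: heart-rate SD 8 to 14 bpm and correlation with baseline 0.7 to 0.3.
- Formula for one visit, adjusted for baseline: SE = SD × √(2/38.5) × √(1 − r²), with √(2/38.5) = 0.228.
- SD 8, r 0.7: SE = 8 × 0.228 × 0.714 = 1.30; 95% half-width 1.96 × 1.30 = 2.6 bpm; difference detectable with 80% power 2.8 × 1.30 = 3.6 bpm.
- SD 14, r 0.3: SE = 14 × 0.228 × 0.954 = 3.04; half-width 6.0 bpm; detectable difference 8.5 bpm.

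**5. Why a mean alone is not enough**
- Illustration: if 2 to 4 of 38 LDQT participants each fell by 20 bpm, the arm mean would move by 2 × 20/38 = 1.1 to 4 × 20/38 = 2.1 bpm. That lies inside the half-width of 2.6 to 6.0 bpm.
- Potassium illustration: one participant rising by 2.0 mEq/L moves the arm mean by 2.0/38.5 = 0.052. With an assumed SD of 0.3 to 0.5 mEq/L, the unadjusted 95% half-width for the arm difference is 1.96 × 0.3 × 0.228 = 0.13 to 1.96 × 0.5 × 0.228 = 0.22. The shift would not be visible.

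**6. What a count would show**
- If the true rate of an out-of-limit value were 5% to 10% (assumed), the chance of seeing at least one among 38 participants is 1 − 0.95³⁸ = 86% to 1 − 0.90³⁸ = 98%.

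**The case against.** The strongest reply is that slow heartbeat is not ignored. It is a listed side effect, listed effects are reported as adverse events, and those feed two modelled safety outcomes. Staff take the pulse at the same visits at which adverse events are collected. This stands, and it rules out the inference that the trial would reach its tolerability conclusion without looking at slow heartbeat at all. What is missing is analysis of the measured rate.

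A reader might also infer that slow heartbeat is the only very common risk specific to LDQT. The table does not support that: leg swelling is very common for amlodipine, which controls receive only conditionally and from week 6. Nor do the frequencies transfer directly to LDQT, since they are for standard doses.

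A third tempting inference is that nobody would act on individual laboratory values or a slow pulse. The documents do not support that either. The adverse event form, AE Reporting Plan, DSMP and Manual of Procedures were not available to this review and may contain trigger rules, and the DSMB may ask for listings. Such rules would still not create pre-specified by-arm outcomes in the SAP.

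Finally, this is a small phase II trial, and SAP section 6 allows further analyses labelled post hoc. True, but that label is a reason to pre-specify now. Counts will be too small for formal comparison, which is why they are proposed as descriptive. The mean and the counts do different jobs: the mean estimates a general shift, and the counts show individuals.

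**Conclusion.** The point holds in a limited form. Measured heart rate is collected at three visits, bears on a listed effect of a drug that only LDQT contains, and is not an outcome in either document. Laboratory safety outcomes are mean changes only. Primary and secondary efficacy inference is unaffected; the gap is in the evidence behind the tolerability conclusion.

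The size is modest. A heart-rate difference could be estimated to within about ±2.6 to ±6.0 bpm, while out-of-limit counts would be informative only as description. The heart-rate SD and correlation, the potassium SD and the event rates are assumptions. The finding itself rests only on comparing the collection schedule with the outcome lists. It is worth changing because the data already exist.

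**What to change.** Add to Protocol 3.3, SAP section 2 and the SAP modelling table:

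1. Change from baseline in heart rate at weeks 6 and 12, analysed by the same baseline-adjusted mixed model as the other continuous outcomes.
2. Number and percentage of participants per arm with heart rate, potassium, sodium, urea or creatinine outside pre-specified limits at any post-baseline visit, reported descriptively. The study team should set the heart-rate limits; for laboratory values, use the laboratory's own limits.

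Naming these as safety outcomes also brings them within the descriptive reports to the DSMB under SAP section 10. Make the change before database lock, so that the analyses need not be labelled post hoc.

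The cost is protocol and SAP wording and a few tables. No new measurement or visit is needed. The downside is that the counts will be small and should not carry formal tests.

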## **6. DATA AND SPECIMEN BANKING**

Data will be collected on paper CRFs and entered into a REDCap database housed at Northwestern University within two business days of collection. The exception is the capture of AEs, which is specified in the AE Reporting Plan. Only study staff with Northwestern NetIDs will have access to the electronic database. We will restrict export rights to the study statistician only. All exports will be housed in secure Northwestern fsmresfiles folder directories with restricted access. These files are routinely backed up through Northwestern’s Information Technology services. Refer to the DSMP and DMP for details on data and safety monitoring and quality checks. Blood and urine samples collected for this study will only be used for this study and will be destroyed after testing.

The results of this trial are not intended to support a New Drug Application (NDA) to bring the LDQT to market in the US. The study team will retain all study records required by applicable regulatory bodies in a secure and safe facility for a minimum period of seven years. Access to study records will be limited to study team members, unless through written application to and approval by the study Steering Committee.

## 7. SHARING RESULTS WITH PARTICIPANTS

When the study is over, research findings will be available at [www.ClinicalTrials.gov](http://www.ClinicalTrials.gov) (Identifier: NCT03640312), as required by US law. After all participants have completed the research study, each participant will receive a letter indicating which study drug he/she received when at randomization. The study staff will host an open forum at the Access Center for Discovery and Learning to share the study results. The study staff will be available to participants if they have questions regarding the results of the study. The research findings will also be published in the form of research articles or presented at scientific meetings. The sponsor, the National Heart, Lung, and Blood Institute of the NIH, requires that these research papers be made freely available to the public through PubMed Central (<https://www.ncbi.nlm.nih.gov/pmc/>) within 12 months of publication with data available thereafter in accordance with NHLBI policy through BioLINCC.

## 8. STUDY TIMELINES

An individual consenting participant will spend a maximum of 12 weeks (three months) participating in the QUARTET USA study. Refer to the study schedule above for details. We anticipate enrollment taking 30 months, assuming an average of 15 participants per month after an initial “ramp up” period. Thus, primary analyses will begin February 2022 with an estimated completion date of November 2022.

